- Thromboembolic events: to be observed over six weeks from the date of surgery
- Hospital stay
- drain output till 72 hours

Methodology

Study Design: A Randomized control trial (RCT)

Setting: Department of surgical oncology, Shaukat Khanum Memorial Cancer Hospital and Research Center, Lahore.

Sample size:

Sample size was calculated on the basis of previous study published by Haase, Douglas R. in 2020. Mean post-operative blood loss in TXA group and non TXA were 981 ± 290 mL and 1542 ± 394 mL, respectively. [02] At 80% power, 95% confidence interval, assuming 10% drop out rate, a total of 36 patients included in this study divided into two groups (18 in each group, TXA versus non TXA) would be required in this study.

Sample selection:**Inclusion criteria:**

Patients with primary or metastatic bone tumors who underwent a resection and an endo-prosthetic reconstruction of the proximal femur, distal femur, proximal tibia and proximal humerus. All patients will be tested for liver function using PT (INR), renal function by serum creatinine and Marrow function by CBC

Exclusion Criteria:

- Patient with a congenital or acquired coagulopathy
- Severe renal or liver insufficiency
- Previous thromboembolic condition
- A patient who received perioperative plasma product
- Pelvic tumor
- Patient who is taking anti-coagulant before surgery
- Patient allergic to tranexamic acid

Enrollment duration: Being a dedicated cancer center, a large number (30-40 per year) of Limb salvage surgeries are performed at Shaukat Khanum Memorial Cancer Hospital. The above-given sample size can therefore be achieved in 10 months.

Dose of tranexamic Acid: A single dose of tranexamic acid will be given intravenously at time of induction according to body weight i.e., 15 mg/kg

Anti-coagulation Protocol: All limb salvage patients started on anticoagulant Injection Enoxaprin subcutaneously after 24 hours of surgery according to body weight i.e. 1.5 mg/kg. Enoxaprin converted to oral tablet Aspirin 75 mg on discharge for 4 weeks.

Study Duration: 12 months after the start of enrollment.

In house admission: Limb salvage surgery patients remain admitted on the floor for an average of 5 days

Follow up Schedule: Physical follow up in clinic 2 weeks after surgery (as per institutional guidelines) and a second follow up at 4 weeks after surgery

Randomization: Intraoperative randomization, patients would be allocated to either of the groups by selecting names from sealed envelopes.

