Type of randomization: Computerized block randomization. This will ensure a similar number of patients in both groups. Patients will have their names written on an envelope with contents of the envelope indicating whether tranexamic acid should be given or not. Only one member of research team will be aware of the contents of the envelope, who will not be present in Operation Theater at the time of surgery and will not take part in data collection. Patient in control group will be given 10 cc of normal saline as as placebo.

Blinding: It will be a triple-blind trial since the patients will be unaware of the group to which they have been randomized. The statistician carrying out data analysis and examiners/interviewers carrying out clinical examinations/interviewing patients will also be unaware of the status of tranexamic acid.

Minimizing Bias: It is not possible to eliminate bias altogether. However, the performance bias of the operating surgeon will be limited by not revealing the contents of the sealed envelope. The interviewer's bias will be limited by ensuring that the interviewer is not aware of tranexamic acid status at the time of the interview and by ensuring a standardized interaction between the patient and interviewer.

Intervention: Surgeon who will carry out Limb salvage surgeries, will be a consultant with > 5-year experience in Limb salvage. A single standardized technique will be used in all of the patients.

There is a difference of opinion about the use of tranexamic acid in surgeons at SKMH and both surgical options are practiced. The trial will therefore pose no additional risks to the patients.

References

- Wei W, Wei B: Comparison of topical and intravenous tranexamic acid on blood loss and transfusion rates in total hip arthroplasty. J Arthroplasty 2014;29:2113-2116

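### As written, the plan does not deliver masking of the surgeon and theatre team: a fixed 10 cc placebo is set against a weight-based drug, and the envelope rules conflict

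*Combined protocol and SAP*

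**What the plan says.** The active drug is given "intravenously at time of induction according to body weight i.e., 15 mg/kg" (Dose of tranexamic Acid). No concentration, diluent or final volume is stated. The comparator has one volume for every patient: "Patient in control group will be given 10 cc of normal saline as as placebo" (Type of randomization).

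On who knows the allocation, Type of randomization says: "Patients will have their names written on an envelope with contents of the envelope indicating whether tranexamic acid should be given or not". It continues: "Only one member of research team will be aware of the contents of the envelope, who will not be present in Operation Theater". That person is also kept out of data collection. The Randomization entry describes the procedure as follows: "Intraoperative randomization, patients would be allocated to either of the groups by selecting names from sealed envelopes".

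The Blinding entry begins "It will be a triple-blind trial since the patients will be unaware of the group to which they have been randomized" and adds the statistician and the examiners or interviewers as the other blinded parties. The surgeon appears under Minimizing Bias, where "performance bias of the operating surgeon will be limited by not revealing the contents of the sealed envelope". Anaesthetic and other theatre staff are not mentioned. The documents do not say who opens the envelope, who draws up the study drug or who gives it, and they describe no pharmacy step, coded label or volume matching.

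The Proforma carries a Group item (drug given or not given) on the same sheet as the haemoglobin, transfusion, drain and blood-loss entries.

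**The concern.** Two features bear on whether the people in theatre can be masked. First, a volume that depends on weight is set against one that does not, so anyone who sees the dose and knows the protocol may be able to tell the arms apart. Second, the allocation has to reach the person drawing up the drug, but the only person permitted to know it is absent.

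This matters because the protocol relies on withholding the allocation from the surgeon to limit performance bias, and because it acknowledges under Intervention that surgeons at the centre disagree about tranexamic acid. The documents state no transfusion criterion, so the number of PRBC units, one of three primary measures, is open to discretion. People in theatre who know the arm could transfuse differently, or make a different haemostatic effort.

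**Working it through.** **Step 1: volumes.** The plan gives no active volume to reproduce; its only volume is the 10 cc placebo. Inputs from the documents are 15 mg/kg and 10 cc. Concentration and body weight are assumptions.

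Volume (mL) = 15 × weight (kg) / concentration (mg/mL), for drug drawn up undiluted.

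| Weight | Dose | At 100 mg/mL | At 50 mg/mL |
|---|---|---|---|
| 40 kg | 600 mg | 6.0 mL | 12.0 mL |
| 60 kg | 900 mg | 9.0 mL | 18.0 mL |
| 70 kg | 1,050 mg | 10.5 mL | 21.0 mL |
| 90 kg | 1,350 mg | 13.5 mL | 27.0 mL |

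The volume equals 10 mL when weight = 10 × concentration / 15, which is 1,000/15 = 66.7 kg at 100 mg/mL and 500/15 = 33.3 kg at 50 mg/mL. The concentration only moves this crossing point. At any single concentration the volume changes 90/40 = 2.25-fold between 40 and 90 kg, while the placebo stays at 10 cc. Below the crossing weight the dose could be diluted up to 10 mL. Above it, the dose cannot fit into 10 mL at all. The plan mentions no make-up volume.

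**Step 2: the envelope rules side by side.**

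- The envelope's contents say whether drug is to be given (Type of randomization).
- Exactly one person knows those contents, and that person is not in theatre during surgery (Type of randomization).
- Allocation from the envelope takes place intraoperatively (Randomization).
- The dose is due at induction (Dose of tranexamic Acid).

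If the envelope is opened in theatre so that the drug can be prepared, a second person learns the allocation, against the second rule. If the informed member prepares the drug beforehand, the allocation was settled before surgery, which does not sit with the third rule. Intraoperative allocation also has to be squared with a dose due at induction. No reading satisfies all four rules without adding a step that the plan does not state.

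**Step 3: which primary outcomes are exposed.** The hemoglobin balance method gives Hb loss = BV × (Hb_i − Hb_e) × 0.001 + Hb_t, with about 52 g Hb per unit. Take one extra discretionary unit and an illustrative BV of 4,000 mL:

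- Hb_t rises by 52 g.
- Hb_e rises by 52 g / 4 L = 13 g/L, so the first term falls by 4,000 × 13 × 0.001 = 52 g.
- Net change in calculated loss: +52 − 52 = 0 g.

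The same unit adds 1 to the PRBC count and reduces the 72-hour haemoglobin drop by 13 g/L. If controls were transfused more readily, the PRBC comparison would shift towards tranexamic acid and the haemoglobin-drop comparison away from it. Calculated loss would be affected mainly if knowledge of the arm changed haemostatic effort, that is, the bleeding itself.

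**Step 4: the Group item.** The informed member takes no part in data collection, yet group is an entry on the data collection form. Either someone else completes it, and so learns the arm, or it is completed later by a route that the plan does not describe. A statistician who receives the form as laid out would see the arm by name.

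**The case against.** The strongest reply is that the blinding the protocol claims covers patients, the statistician and the examiners, and none of these depends on a syringe. The patient receives the dose at induction, the statistician never sees it, and examiners can be kept apart from theatre. The surgeon's masking is offered only to limit bias, in a section that concedes bias cannot be removed entirely. A reader might infer from the volume mismatch that the triple-blind claim fails as a whole. The documents do not support that, and this part of the reply stands.

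A reader might also infer that someone in theatre is bound to open the envelope. That goes too far: the text keeps the informed member out of theatre during surgery but does not bar that person from preparing a coded syringe beforehand. Advance preparation is unstated rather than excluded. It still conflicts with intraoperative allocation, so the passages need reconciling on either reading.

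The volume argument needs a concentration that the documents do not give, and an observer who sees the dose and can interpret it. At an assumed 100 mg/mL, patients of 60 to 73 kg would receive 9.0 to 10.95 mL, which is hard to tell from 10. This limits how many patients are affected. It does not remove the mismatch, because weight-dependence remains at every concentration unless both arms are made up to a common volume.

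Finally, it is tempting to say that biased transfusion carries through to calculated blood loss because PRBC units enter the formula. Step 3 shows that it largely cancels, provided BV is held constant and the unit contains the assumed haemoglobin.

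**Conclusion.** The concern holds for the surgeon and theatre team. The stated arrangements do not deliver their masking: active and placebo volumes agree at only one body weight for any single undiluted concentration, and the rules on who knows the allocation, when it is drawn and when the drug is given conflict. The millilitre figures rest on assumed concentrations and weights; the existence of a single crossing point does not.

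Failure of patient, statistician or examiner blinding is not shown on this ground. Separately, the open Group item could reveal allocation to data collectors and the statistician, although the documents do not show that it would.

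Two primary outcomes, PRBC units and the 72-hour haemoglobin drop, are directly exposed to transfusion decisions by unmasked staff. Calculated loss is exposed mainly through haemostatic effort. The documents give no basis for putting a size on the resulting bias. The point should be corrected, because primary outcomes are exposed and the remedy is cheap.

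**What to change.** Reconcile the Randomization, Type of randomization, Dose of tranexamic Acid and Minimizing Bias entries in one paragraph stating that:

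- allocation takes place before induction;
- the informed team member whom the plan already provides for prepares the study drug outside theatre;
- both arms are made up to the same total volume, large enough to hold the protocol dose for the heaviest patient, in identical containers labelled only with the randomisation number;
- theatre staff give the coded container and open no envelope that shows the allocation.

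Take the Group item off the outcome proforma, hold it in a separate allocation list, and give the statistician coded arms. The tranexamic acid dose stays as the protocol states it.

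The cost is a short protocol change and a few minutes of preparation per case; the downside is that the informed member must be available before every operation. If enrolment has begun, document how the study drug was actually prepared and given and who knew the allocation, and describe the blinding in the report accordingly.

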- Femur _____
- Tibia _____
- Other

Group:

- Tranexamic Acid Given
- Tranexamic Acid Not Given

Length of Bone Resected _____ **Cm**

Wound Healing: (Satisfactory / Unsatisfactory)

Preoperative Hemoglobin _____gms

Preoperative INR _____

Intraoperative Blood Loss: _____mls

Postoperative Hemoglobin after 24 Hours _____gms

Postoperative Hemoglobin after 72 Hours _____

Number of PRBC Transfused Within 72 Hours of Surgery _____

Blood Loss Calculated By Direct Hemoglobin Method _____

Drain Output in 72 Hours: _____mls

Any Thromboembolic Event: _____

Status of Ambulation:

STATISTICAL ANALYSIS PLAN:

Statistician independently pooled data from each case then conducted statistical analysis using SPSS Descriptive data are presented as mean \pm standard deviation (*SD*). Odds ratio (*OR*) with 95% confidence intervals (*CI*) or mean differences (*MD*) with 95% *CI* were calculated for dichotomous and continuous outcomes, respectively. Numerical and measured data were compared using a *t*-test and χ^2 -test, respectively. An appropriate power and sample size calculator was used to calculate statistical power. The following parameters were used in the calculations: α , probability of a type I error for a two-sided test; P_0 , probability of exposure in controls; N , number of patients; m : ratio of control to experimental subjects; and Ψ , odds ratio of exposure in experimental subjects relative to controls. $P < 0.05$ was considered significant.

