Despite ample research documenting the safety and efficacy of perioperative TXA in patients undergoing arthroplasty, there is no known clinical trial focusing on TXA's use in musculoskeletal oncology patients undergoing endoprosthesis reconstruction. Nonetheless, TXA is used within the musculoskeletal oncology community, with its use varying from surgeon to surgeon. Surgeons who use TXA do so with the intent of limiting perioperative blood loss and transfusion rates in these high blood-loss procedures. However, without clinical trial to support its use in this cohort, these patients, who tend to have an increased number of comorbidities, could be inheriting an increased risk of perioperative complication without the benefits documented. Conversely, patients within this cohort that do not receive TXA could be missing out on the clinical benefits of TXA seen in patients undergoing arthroplasty. This randomized clinical trial will determine the efficacy of tranexamic acid in musculoskeletal oncology population who underwent wide local excision and reconstruction with endoprosthesis and will result in the formation of a guideline about its efficacy in reducing blood loss and adverse events that can be resulted by the use of tranexamic acid in the musculoskeletal oncology population.

Objectives:

To determine the efficacy of tranexamic acid in musculoskeletal tumor who underwent wide local excision and reconstruction with endoprosthesis and determine adverse events that can be resulted by the use of tranexamic acid.

Primary outcome measures:

Blood loss in a surgical patient can be monitored by:

- Drop-in hemoglobin in 72 hours
- The number of transfused PRBC unit
- 72-hour total blood loss as calculated by hemoglobin balance method

Hemoglobin balance method:

The Hemoglobin - balance method is based on the balance of Hemoglobin during the perioperative period of surgery. It is regarded as an important method with intuitive expressiveness and high accuracy and often addresses contemporary clinical issues [14]

$Hb_{\text{loss total}} = BV \times (Hb_i - Hb_e) \times 0.001 + Hb_t$	$Hb_{\text{loss total}}$ (g): The loss volume of Hb
$V_{\text{loss total}} = 1000 \times Hb_{\text{loss total}} / Hb_i$	Hb_i (g/L): The Hb value before surgery
Generally, 1 U banked blood is considered to contain 52 ± 5.4 g Hb[5]	Hb_e (g/L): The Hb value after surgery;
	Hb_t (g): The total volume of blood transfusion

Secondary outcome measures:

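### The SAP's only effect measure for dichotomous outcomes, the odds ratio, is 0, infinite or undefined for thromboembolic events whenever an arm has none, and no rule covers that case

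*Combined protocol and SAP*

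**What the plan says.** The Statistical Analysis Plan, at the end of the combined protocol and SAP, sets the effect measures in one sentence: "Odds ratio (*OR*) with 95% confidence intervals (*CI*) or mean differences (*MD*) with 95% *CI* were calculated for dichotomous and continuous outcomes, respectively". The next sentence sets the tests: "Numerical and measured data were compared using a *t*-test and χ^2 -test, respectively". The section names no exact method, continuity correction, risk difference or rule for an arm without events.

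Harm is part of the stated aim. Under Objectives the trial is also to "determine adverse events that can be resulted by the use of tranexamic acid". The secondary outcomes include "Thromboembolic events: to be observed over six weeks from the date of surgery", and the proforma has one entry for any such event, which supports a yes/no outcome.

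The Sample size section, "assuming 10% drop out rate, a total of 36 patients included in this study", puts 18 in each arm. No expected thromboembolic rate appears anywhere; the control probability and odds ratio in the SAP's power paragraph are symbols without values.

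**The concern.** An odds ratio needs events in both arms. If one arm has none, the estimate is 0 or infinite; if neither has any, it is 0/0. The usual interval on the log odds ratio cannot be computed in any of these cases, and with no events at all the chi-square statistic is undefined too. At 18 per arm this can easily happen if events are uncommon. The planned safety comparison would then give no usable estimate, and the analyst would have to choose a replacement after seeing the data. A result with no events in either arm could also be read as evidence of safety, with no interval to show how little it rules out.

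The test sentence adds confusion. Taken as worded, it pairs measured data with the chi-square test, while the sentence before it gives continuous outcomes a mean difference. If *numerical* was meant as counts or categories, the two tests are in swapped order. Either way the wording conflicts with its neighbour.

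**Working it through.** **Inputs.** From the documents: 18 per arm, 10% dropout (18 × 0.9 = 16.2, so about 16 evaluable per arm), and the odds ratio as sole effect measure. Assumed: true event rates p of 2%, 5%, 10% and 20%, and independent binomial arms.

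**The plan's own figures.** There is none for thromboembolic events. The stated total of 36 does not follow from its stated inputs. The difference is 1542 − 981 = 561 mL and the SD is √((290² + 394²)/2) = 345.9 mL. At two-sided 5% and 80% power a t-test needs 8 per arm; 8/0.9 rounds up to 9, or 18 in total. The plan is larger than those inputs require. That is a separate matter, and 18 per arm is taken here as stated.

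**Chance of an empty arm.** Let q = (1 − p)^n. Then P(at least one arm empty) = 1 − (1 − q)², P(both empty) = q², and P(control arm empty) = q.

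| Assumed rate, both arms | At least one empty, n = 18 | Both empty, n = 18 | Control arm empty, n = 18 | At least one empty, n = 16 |
|---|---|---|---|---|
| 2% | 91% | 48% | 70% | 92% |
| 5% | 64% | 16% | 40% | 69% |
| 10% | 28% | 2% | 15% | 34% |
| 20% | 4% | 0.03% | 2% | 6% |

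Example at 5%: q = 0.95^18 = 0.397, and 1 − 0.603² = 0.637.

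The chance passes 50% when q = 1 − √0.5 = 0.293, so p = 1 − 0.293^(1/18) = 6.6% (7.4% at 16 per arm). With unequal rates it is 82% at 5% v 2% and 49% at 10% v 5%.

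**Would an exact odds-ratio interval help?** Only in part. With one event in all and equal arms, the chance that it falls in the TXA arm is ψ/(1 + ψ), where ψ is the odds ratio.
- TXA 0 v control 1: 1/(1 + ψ) = 0.025 gives an interval of 0 to 39.0, which is finite.
- 1 v 0: ψ/(1 + ψ) = 0.025 gives 0.026 to infinity.
- 2 v 0: 0.19 to infinity.
- 0 v 0: 0 to infinity.

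So the upper limit is infinite whenever the control arm is empty, alone or with the other. That is the q column above.

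**Risk difference, 18 per arm.** The Newcombe interval combines the two Wilson intervals. For 0 of 18 the Wilson upper limit is 3.84/(18 + 3.84) = 0.176.
- 0 v 0: −17.6 to +17.6 points (exact unconditional: about −18.5 to +18.5).
- 1 v 0: −12.6 to +25.8 points (exact unconditional: about −13 to +27).
- 2 v 0: 11.1 points, Newcombe −8.2 to +32.8.

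**Haemoglobin drop.** The outcome "Drop-in hemoglobin in 72 hours" contains the pre-operative value, which the proforma records. Let k be the ratio of post- to pre-operative SD and ρ the within-arm correlation between them. The correlation of the drop with the pre-operative value is r = (1 − kρ)/√(1 + k² − 2kρ), and the adjusted-to-unadjusted variance ratio is (1 − r²)(N − 3)/(N − 4). With N = 36 and assumed ρ of 0.3, 0.5, 0.7 and 0.9:
- k = 1: 0.67, 0.77, 0.88, 0.98.
- k = 1.25: 0.81, 0.92, 1.01, 0.98.

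At r = 0 the ratio is 33/32 = 1.03. Break-even is r = √(1/33) = 0.17.

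**The case against.** The strongest reply is that the frequency is assumed. That stands. The plan excludes "Previous thromboembolic condition" and gives routine prophylaxis ("All limb salvage patients started on anticoagulant"), which suggests few events. But the Introduction also cites the concern that TXA promotes clotting and describes these patients as having more comorbid disease. None of this sets a rate, and at 10% or more an empty arm is possible but not likely.

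Second, the odds ratio is not useless in every such case. When only the TXA arm is empty, an exact interval has a finite upper limit. At an assumed 5% rate these cases make up 24 of the 64 percentage points (half of the 48% with exactly one empty arm). This stands and narrows the problem, though the SAP names no exact method.

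Third, the Blinding section keeps the statistician unaware of treatment status, so a late choice of method could not easily favour one arm. This lessens the risk of a biased choice. It does not supply the missing estimate.

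A reader might infer from the test sentence that blood loss would be analysed by chi-square and the primary analysis is invalid. The documents do not support that: the sentence just before assigns continuous outcomes a mean difference with a CI, so the wording is a slip. Nor is the unadjusted t-test wrong for haemoglobin drop; adjustment only adds precision, and under some assumptions it adds none.

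**Conclusion.** The gap is certain; how often it would bite is not known. The SAP's rule gives 0, infinity or no value for thromboembolic events whenever an arm has none, and no alternative is specified. At 18 per arm the chance is 91%, 64%, 28% or 4% at assumed equal rates of 2%, 5%, 10% or 20%, and exceeds one half only below about 6.6%. A reader might conclude that the safety comparison will probably fail. Without an event rate, the documents do not support that unconditional statement.

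The point concerns a secondary safety outcome, although one that the Objectives name. It leaves the primary blood-loss comparison untouched. No method makes 36 patients informative about uncommon harms; a finite interval such as ±17.6 points for no events in either arm at least shows how little is known. It is worth correcting before the data are seen.

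**What to change.** Replace both the effect-measure sentence and the test sentence. Changing only the second would leave the unconditional odds-ratio rule in force and in conflict with the new text. Suggested wording:

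> Continuous outcomes are compared by t-test and reported as mean differences with 95% CI; haemoglobin drop is analysed by a linear model with treatment and pre-operative haemoglobin. Dichotomous outcomes, including thromboembolic events, are reported as counts per arm and the risk difference with a 95% CI that stays finite with zero events [Newcombe or exact unconditional: name one in advance], which carries the safety conclusion. An odds ratio is given only when both arms have events. A non-significant p-value, or the absence of events, is not read as evidence of safety.

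Either interval will do. Adjusting 72-hour blood loss is not requested: its formula divides by pre-operative haemoglobin, so the correlation may be near zero and no gain has been shown. A switch to Fisher's test is not requested either.

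The cost is SAP wording and no new data. The haemoglobin model uses one degree of freedom, so its variance is about 3% larger if the pre-operative value is uncorrelated with the drop. The interval may need software other than SPSS.
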